3.5 Study Outcomes

3.5.1 Data Collected

The following data will be collected from medical records and will be recorded in the electronic case report form (eCRF) by investigators (or designees) during the study period:

- Informed consent
- Demographics: age at start of afatinib (Gi(l)otrif[®]) treatment, gender, ethnicity and race
- Type of mutations at initial diagnosis
- Stage of disease (IIIb or IV) at start of afatinib (Gi(l)otrif[®]) treatment
- Sites of metastases at start of afatinib (Gi(l)otrif[®]) treatment
- Eastern Cooperative Oncology Group (ECOG) performance score (PS) (if available) at start of afatinib (Gi(l)otrif[®]) treatment
- Body weight and height at start of afatinib (Gi(l)otrif[®]) treatment
- Date of start and end of afatinib (Gi(l)otrif[®]) treatment
- Starting dose of afatinib (Gi(l)otrif[®])
- Afatinib (Gi(l)otrif[®]) dose modification(s) and respective date(s)
- Reason for discontinuation of afatinib (Gi(l)otrif[®]) treatment (e.g. progressive disease (PD), adverse event (AE))
- Type of mutations at start of osimertinib treatment
- Sites of metastases at start of osimertinib treatment
- ECOG PS (if available) at start of osimertinib treatment
- Type of mutations at stop of osimertinib if available (EGFR mutations: T790M, C797S [if positive: in cis or in trans], Del19, L858R, other EGFR sensitizing mutation (to be specified), non-EGFR: to be specified) (R16-1552, P15-11024)
- If osimertinib was provided within an EAP/CUP or prescribed as clinical practice
- Date of start and end of osimertinib treatment
- Starting dose of osimertinib
- Osimertinib dose modification(s) and date(s)
- Reason for discontinuation of osimertinib treatment (e.g. PD, AE)
- Subject status at data entry completion
- Date of death (if available) / Date patient was last known to be alive (if available)
- Date of consent withdrawal (if applicable)
- All ADRs (independently from the outcome) and AEs with fatal outcome with respective start and end dates, severity, outcome, seriousness and relationship to afatinib (Gi(l)otrif[®])

3.5.2 Primary Outcome

Time on treatment with afatinib (Gi(l)otrif[®]) followed by osimertinib.

This will be assessed as the time from start of afatinib (Gi(l)otrif[®]) as first-line treatment until the end of the second-line treatment (last dose of osimertinib) or death date by any cause.

Statistical Analysis Plan Template For Observational Studies

Boehringer Ingelheim
Protocol c14668275-02

Statistical Analysis Plan

3.5.3 Secondary Outcome

Type and proportion of acquired resistance mutations after osimertinib.

4 DATA SOURCE

Data will be collected from patients' medical records and recorded in (e)CRFs.

4.1 Source documents

Source documents provide evidence for the existence of the patient and substantiate the integrity of the data collected. Source documents are filed at the investigator's site. Data entered in the eCRFs that are transcribed from source documents must be consistent with the source documents or the discrepancies must be explained. The investigator may need to request previous medical records or transfer records, current medical records must be available.

For (e)CRFs all data must be derived from source documents.

4.2 Records

The CRFs for individual patients will be provided via remote data capture (RDC) system or Electronic Data Capture (EDC) system.

4.3 Direct access to source data and documents

The investigator / institution will permit study-related monitoring, audits, Institutional Review Board (IRB) / Independent Ethics Committee (IEC) review and regulatory inspection, providing direct access to all related source data / documents. eCRFs and all source documents, including progress notes and copies of laboratory and medical test results must be available at all times for review by Boehringer Ingelheim (BI's) clinical study monitor, auditor and inspection by health authorities (e.g. FDA). The clinical research associate (CRA)/on site monitor and auditor may review all eCRFs, and written informed consents (if applicable). The accuracy of the data will be verified by reviewing the documents described in Section 4.1.

4.4 Storage of records

The study site(s) must retain the source documents and essential documents according to contract or the local requirements valid at the time of the end of the study (whatever is longer).

Statistical Analysis Plan Template For Observational Studies

Boehringer Ingelheim
Protocol c14668275-02

Statistical Analysis Plan

5 STATISTICAL METHODS

5.1 Data Quality Assurance

All entries in the eCRF will be stored in a database. The structure of the database is based on the division into sections and entry fields defined in the eCRF. To improve and ensure data quality, data checks will be performed automatically in the eCRF directly on electronic entry at the study site.

Plausible value ranges for numerical data entries and logical data and list entries will be filed in the eCRF. The tests for consistency and completeness based on this will be performed during entry in the eCRF. The validity of the recorded data will therefore be ensured by the validations incorporated in the documentation system, which highlight incorrect or implausible entries to the data entry clerk/doctor.

If corrections are necessary after the data are saved, these will be documented in an audit trail.

For the further quality assurance of the documented patient observations, a sample-size based source data verification will be performed on about 30% of included patients.

Patient replacement may be considered if there are major quality issues (e.g. accuracy of the data or data validity cannot be trusted or enrolled the patient has too many missing data) identified from the collected data. The decision of whether or not to enforce a patient replacement will be made by BI and the study team after evaluations. Data of the replaced patients will not be included in the final data analysis.

A quality assurance audit/inspection of this study may be conducted by BI or BI's designees or by IRBs/IECs or regulatory authorities. The quality assurance auditor will have access to all medical records, the investigator's study-related files and correspondence, and the informed consent documentation of this study.

All tables, figures and data listings to be included in the report will be independently checked for consistency, integrity and in accordance with standard procedures for analysis and reporting.

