3 STUDY DESIGN

This is a non-interventional, multi-country, multi-centre cohort study based on existing data from medical records of patients with EGFR mutation-positive advanced NSCLC treated with afatinib (Gi(l)otrif[®]) as the first-line treatment followed by osimertinib in case the T790M resistance mutation was developed.

In total, at least 190 eligible patients are planned to be enrolled to this study.

Key study outcome:

The time on treatment with afatinib (Gi(l)otrif[®]) followed by osimertinib.

Statistical Analysis Plan Template For Observational Studies

Boehringer Ingelheim
Protocol c14668275-02

Statistical Analysis Plan

It is planned that around 65 study centres in 11 countries will be participating in this non-interventional study (NIS) and at least 190 consecutive eligible patients will be enrolled to the study. Every patient who fulfils inclusion and exclusion criteria and agree to participate in the study (if a written informed consent is required for this NIS by local regulation and legal requirement) will be selected until the required sample size is achieved. Deceased patients should be enrolled whenever possible.

Recruiting of patients for this study is competitive, i.e., recruitment will stop at all centres when it is determined that a sufficient number of patients have been enrolled.

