3.2 Full Analysis Set

The full analysis set (FAS) includes all patients who were enrolled into the study, met all inclusion criteria and did not meet any exclusion criteria and provided a written and signed informed consent (if a written informed consent is required for this NIS by local regulation and legal requirement). The FAS will be used for all the analyses performed during this study.

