5.8 Handling of Missing and Incomplete Data

In case of missing data for any variable, the information on the number of patients with missing data will be displayed in the appropriate output(s). For categorical variables, the percentages will be calculated based on all available data (missing and non-missing). The subjects with missing information will be included in the calculations.

Regarding the analysis of the primary outcome, it is not expected to have missing information regarding the start date of afatinib (Gi(l)otrif[®]) treatment. For patients still on treatment, time on treatment will be censored at the date of completion of data collection. For patients lost to follow-up and still on treatment, time on treatment will be censored at the date the patient was last known to be alive.

The possibility of having missing date for ECOG PS is foreseen and no imputation rules will be applied.

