5.8.1 Partial Dates

The following dates will be collected completed (no partial dates are accepted) in the CRF: 'date of visit' (date of the first day of data entry), 'date of informed consent', 'date of date entry completion' and 'date of consent withdrawal'. For the other dates, the following rules will be applied.

In case the day is missing and the month and year are given:

- the 15th of the month for:
 - Start date of initial dose (afatinib (Gi(l)otrif[®]))

Statistical Analysis Plan Template For Observational Studies

Boehringer Ingelheim
Protocol c14668275-02

Statistical Analysis Plan

- the end day of last dose of afatinib (Gi(l)otrif[®]) if the month and year are same otherwise the 15th of the month for:
 - Start date of initial dose (osimertinib)
- the end day of the previous dose if the month and year are the same otherwise the 15th of the month for:
 - Start date of modified dose (afatinib (Gi(l)otrif[®]))
 - Start date of modified dose (osimertinib)
- the start day of the next dose if the month and year are the same otherwise the 15th of the month for:
 - End date of initial dose (afatinib (Gi(l)otrif[®]))
 - End date of initial dose (osimertinib)
 - End date of modified dose (afatinib (Gi(l)otrif[®]))
 - End date of modified dose (osimertinib)
- The day of last dose of osimertinib if the month and year are the same otherwise the 15th of the month for:
 - Date of death
 - Date patient was last known to be alive

If day and month are missing and year is given:

- The day and month of last dose of osimertinib if the year is the same otherwise the 1st of January for:
 - Date of death
 - Date patient was last known to be alive

In case the end date of one dose and start date of the next dose are partially given and they are the same (e.g. September 2017), is assumed the 15th day of the month for the former and the 16th day for the latter.

The same is assumed for the end date of afatinib (Gi(l)otrif[®]) and start date of osimertinib.

Patients with a substantial amount of missing and/or partial dates may be replaced according to section 5.1.

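### SAP 5.1 and 5.8.1 allow eligible enrolled patients to be dropped from the final analysis for missing or partial dates, against the FAS in 3.2, with no fixed criterion, disposition row or analysis that keeps them

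*SAP*

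**What the plan says.** **Analysis set.** SAP 3.2 defines the FAS as enrolled patients who satisfy the eligibility criteria, with consent where local rules require it. It then states: "The FAS will be used for all the analyses performed during this study". No exception for data quality is given. SAP 3 plans that "at least 190 consecutive eligible patients will be enrolled to the study", and SAP 3.1.3 says that all qualifying patients at a site are entered, so that bias is avoided.

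**Replacement.** SAP 5.1 says: "Patient replacement may be considered if there are major quality issues". Its examples are data that cannot be trusted and a patient with too much missing. On who decides and when: "The decision of whether or not to enforce a patient replacement will be made by BI and the study team after evaluations". The consequence is: "Data of the replaced patients will not be included in the final data analysis". SAP 5.8.1 adds: "Patients with a substantial amount of missing and/or partial dates may be replaced according to section 5.1".

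**Date rules.** SAP 5.8 censors patients still on treatment at completion of data collection. For a second group it says "For patients lost to follow-up and still on treatment, time on treatment will be censored at the date" last known alive. SAP 5.8.1 imputes a missing day for treatment, death and last-alive dates. Its rule headed "If day and month are missing and year is given" covers only death and last known alive.

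**Disposition.** SAP 5.3 promises a full accounting. T14.1.1.1 gives reasons for non-inclusion (eligibility only), T14.1.1.2 gives inclusions by centre, country and region, and T14.1.1.3 gives deaths, non-completers and follow-up time.

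**The concern.** A patient can meet every condition of 3.2 and still be left out under 5.1 or 5.8.1, so the two rules cannot both hold.

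The ground for removal is not neutral to the endpoint. SAP 5.6.1 builds time on treatment from the afatinib start date, the osimertinib end date and the death date. A patient whose dates are poorly recorded may differ in time on treatment from one whose dates are complete. With one group and no comparator (SAP 3.3.2), any such selection falls directly on the reported median.

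The people who decide will have evaluated the collected data, and nothing keeps time on treatment or censoring status from them. A reader of the report would have no named output stating how many patients were removed or why.

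**Working it through.** **1. The plan's own figure.** SAP 5.9 needs 171 patients for an 80% chance that the 90% CI for the median is at most 10 months wide (exponential, median 24), and allows for 10% censoring: 171/(1 − 0.10) = 190. In simulation with the Kaplan-Meier log-log interval, 171 uncensored patients give 80.5%, and 190 with 10% censoring give 80.8%. The figures reproduce, and the concern does not depend on them. They contain no allowance for replaced patients.

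**2. Which patients have no stated rule except possible replacement.**

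| Situation | Rule in the SAP |
|---|---|
| Still on treatment | Censored (5.8) |
| Lost while on treatment | Censored (5.8) |
| Day missing, month and year known | Imputed (5.8.1) |
| Death or last-alive date, year only | Imputed (5.8.1) |
| Death recorded, osimertinib end date missing | Death is an event by the 5.6.1 definition |
| Treatment date, year only | None |
| Known to have stopped, no end date, no recorded death | None |

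**3. Size of a selection effect.** From SAP 5.9: exponential, median 24, n = 190. Assumed, because the SAP gives no replacement rate: k = 10 removed, and 10 added at random from the same population. Write S for survival and F = 1 − S. The analysed median is where 95 of the 190 expected patients lie on each side.

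- All 10 removed from below the median: for t > 24, 190S + 10S = 95, so S = 95/200 = 0.475 and t = −(24/ln 2)·ln 0.475 = **25.8**.
- All 10 removed from above: for t < 24, 200F = 95, so S = 0.525 and t = **22.3**.
- 8 below and 2 above: the two removed above are spread as 2·S/0.5 = 4S, so (190 − 4 + 10)S = 196S = 95, S = 0.4847 and t = **25.1**.
- 2 below and 8 above: 196F = 95, so S = 0.5153 and t = **23.0**.
- 5 and 5: (190 − 10 + 10)S = 95, so t = **24.0**, no shift.
- k = 5, one-sided: 195S = 95 or 195F = 95, giving 24.9 or 23.1.

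**4. A second selection model.** Let a fraction f of patients be removed, with their own exponential median m, while the whole population has median 24. The retained median M solves (1 − f)·2^(−24/M) + f·2^(−24/m) = 0.5.

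| Removed (assumed) | m = 12 | m = 36 |
|---|---|---|
| 2% (about 4) | 24.4 | 23.8 |
| 5% (about 10) | 24.9 | 23.5 |
| 10% (19) | 26.0 | 23.0 |

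The two models agree on about 1 month or less for 5% removed, short of one-sided removal.

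**5. Against sampling error.** In the simulation the typical 90% CI width at n = 190 uncensored is about 8.3 months, so SE ≈ 8.3/(2 × 1.645) ≈ 2.5. A shift of 25.08 − 24 = 1.08 months is about 0.4 SE.

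**The case against.** - **The rule is more restrained than it may sound.** It is permissive, applies to major issues, and requires a substantial amount of missing or partial dates. A reader might infer that any partial date leads to removal, or that patients without an osimertinib end date are generally dropped. The SAP does not say so: ordinary partial dates are imputed, and patients still on treatment or lost while on treatment are censored.
- **Excluding data that cannot be trusted is legitimate.** This stands, and the fix keeps it. Verifying treatment dates means looking at them, so strict blindness to those dates is not practicable. What can be required is that the criterion is fixed before the endpoint variable is derived.
- **Disposition is partly covered.** Listing L16.2.1.1 includes everyone checked for entry, and the display details sit in separate TLF shells. A replaced patient may therefore appear in the listing, but the SAP specifies no replacement flag, reason or count.
- **The protocol, which is not shown, may hold operational criteria.** It may, but the conflict between 3.2 and 5.1/5.8.1 lies within the SAP.
- **The effect is small and assumption-driven.** Neither 10 of 190 nor the 8:2 split is in the SAP, and the resulting shift is well inside the confidence interval. This stands and limits the severity. It does not remove the conflict, and a systematic shift is not reflected in the interval's width.

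**Conclusion.** The point holds as a conflict over who is analysed, and should be corrected. SAP 3.2 keeps all eligible enrolled patients, while 5.1 and 5.8.1 allow some to be left out on an unquantified ground that acts on the dates forming the primary endpoint. No named output or analysis shows the effect.

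The likely size is modest: about 1 month on a 24-month median at 8:2, and 1.7 to 1.8 months at the one-sided extremes. Both rest on an assumed 10 of 190 removed, exponential times and random replacements. If removal is unrelated to time, the shift is zero.

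A reader might infer that the reported median will be inflated, or that the rule exists to favour a result. The SAP supports neither. The direction is unknown and no replacement rate is given.

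**What to change.** 1. **SAP 5.1 and 5.8.1:** delete missing or partial dates as a ground for exclusion. Keep these patients in the FAS as 3.2 states, and count any added patients as additional.
2. **SAP 5.1 and 3.2:** allow removal only where the data are judged not trustworthy, by a written criterion fixed before the time-on-treatment variable is derived. State this exception in 3.2.
3. **SAP 5.3 and 5.6.1:** add a row to T14.1.1.3 for patients removed after enrolment, by reason. Add a sensitivity Kaplan-Meier analysis that includes any removed patient with recorded endpoint dates.
4. **SAP 5.8 and 5.8.1:** where death is recorded and the osimertinib end date is missing, say explicitly that the death date is the event, as 5.6.1 defines. For year-only treatment dates, and for patients known to have stopped with no end date and no recorded death, keep the event. Run Kaplan-Meier at the earliest and the latest feasible date. For a missing osimertinib end date, the earliest is the last documented osimertinib dosing date (start or last dose modification) and the latest is last known alive or data entry. Name in advance which date the primary run uses, and report both bounds beside it.

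**Cost:** SAP wording, one table row and a few extra runs on data already collected. A few imputed dates add measurement error, and the bounds may be wide because SAP 3.5.1 collects few dates within treatment. In simulation with 10 such patients, the earliest bound moved the median by as much as about −1.3 months (last documented dosing date assumed at 57% of true time). The latest moved it by as much as about +1.6 (12-month median gap to the upper date assumed). A single midpoint date is not a safe substitute for the bounds. With an assumed 24-month median gap it shifts the median by about +0.8 months even when the affected patients are a random subset, where replacement gives no shift.

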5.2 General Presentation Considerations

No study visits are expected on this study. The 'Date of Visit' page in eCRF will include only the information of the first day of data entry.

Continuous data will be summarized in terms of the mean, standard deviation (SD), median, minimum, maximum and number of observations, unless otherwise stated. Continuous data that are expected to be skewed will be presented in terms of the maximum, upper quartile, median, lower quartile, minimum and number of observations. The minimum and maximum will be reported to the same number of decimal places as the raw

Statistical Analysis Plan Template For Observational Studies

Boehringer Ingelheim
Protocol c14668275-02

Statistical Analysis Plan

data recorded in the database. The mean, median, lower quartile and upper quartile will be reported to one more decimal place than the raw data recorded in the database. The SD will be reported to two more decimal places than the raw data recorded in the database. In general, the maximum number of decimal places reported shall be four for any summary statistic. The number of decimal places to be displayed in each output will be specified in the Tables, Listings and Figures (TLF) shells document.

Categorical data will be summarized in terms of the number of patients providing data at the relevant time point (n), frequency counts and percentages. The number of patients with missing information for a specific variable will be displayed if applicable. Any planned collapsing of categories will be detailed in the SAP text and the data displays. Percentages will be presented to one decimal place. Percentages will not be presented for zero counts. Percentages will be calculated using non-missing data as the denominator.

Confidence intervals will be presented to one more decimal place than the raw data.

All report outputs will be produced using SAS® version 9.3 or a later version in a secure and validated environment. All report outputs will be provided to BI in a single Microsoft Word document.

5.3 Study Patients

A clear accounting of the disposition of all patients who enter the study will be provided.

- A summary of the number of patients checked for entry into the study and the number and percentage of patients not included by major reason – not meeting an Inclusion criterion or meeting an Exclusion criterion – and overall T14.1.1.1
 - A summary of the number and percentage of patients included - per center, per country and region T14.1.1.2
 - A summary of the number and percentage of dead patients and patients not completing the study, as well as the follow-up time in the study, calculated as below. T14.1.1.3
- Follow – up Time (months) = (Data entry completion date – Start date of afatinib)/30.4375*

Two by-patient listings will be provided:

- For all patients checked for entry, one listing will be presented with the date of first day of data entry, the Inclusion and Exclusion criteria and date of informed consent (if applicable) L16.2.1.1
- For all patients included in the study, one listing with the status at data entry completion will be presented. This listing will include at least the subject status and data of death / lost to follow-up (if applicable) L16.2.1.2

Statistical Analysis Plan Template For Observational Studies

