This table will be repeated for the following subgroups: Ethnicity, Race, EGFR mutation, Gender, Brain metastases at start of Afatinib, Brain metastases at any time, Age group 1, Age group 2, ECOG and Data Source. T14.2.3.4

Time between end of afatinib and start of osimertinib will be summarized through descriptive statistics. T14.2.3.15

Time between end of osimertinib and death will be analyzed in a similar way as the primary outcome. T14.2.3.16
F14.2.3.17

Swimmer plots displaying time on afatinib treatment, time between end of afatinib and start of osimertinib and time in osimertinib treatment for each patient will be provided. F14.2.3.18

By-patient listings will be provided including at least the time on treatment (afatinib, osimertinib and total), time between end of afatinib and start of osimertinib, time between end of osimertinib and death and information whether the patient was censored or not. L16.2.6.6
L16.2.6.7
L16.2.6.8

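### Follow-up time runs past death and loss to data entry completion, and year-only death dates are set to the earliest possible day

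*SAP*

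**What the plan says.** Section 5.3 (Study Patients) plans one table, T14.1.1.3, with the "number and percentage of dead patients and patients not completing the study, as well as the follow-up time in the study". Follow-up has a single formula for all patients: ("Data entry completion date – Start date of afatinib")/30.4375.

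Other sections bear on this:

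- Section 3 (Study Design): "Deceased patients should be enrolled whenever possible".
- Section 3.5.1 (Data Collected) lists "Date of death (if available) / Date patient was last known to be alive (if available").
- Section 5.8 (Handling of Missing and Incomplete Data), for patients lost while still on treatment: "time on treatment will be censored at the date the patient was last known to be alive".
- Section 5.8.1 (Partial Dates), for a death or last-alive date with only the year known: "The day and month of last dose of osimertinib if the year is the same otherwise the 1st of January for" these two dates. If only the day is missing: "The day of last dose of osimertinib if the month and year are the same otherwise the 15th of the month for" the same two dates.
- Section 5.6.1 (Analysis of the Primary Outcome): "Time between end of osimertinib and death will be analyzed in a similar way as the primary outcome", that is, by Kaplan-Meier (T14.2.3.16, F14.2.3.17).

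**The concern.** **Follow-up.** Months after death or loss are counted as follow-up. The patients for whom this is wrong are reported in the same table and are enrolled on purpose. A reader will use the figure to judge how mature the data are. The SAP itself cares about maturity: section 3.1.3 justifies the 10-month threshold by the wish to avoid early censoring.

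**Year-only deaths.** A death cannot precede the last dose. The imputed date is therefore always the earliest one possible, and the error can only go one way. When death and last dose fall in the same year, the time from osimertinib end to death becomes exactly zero, so false events at time zero enter the curve.

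**Year-only last-alive dates.** The same rule supplies the primary censoring date for a patient lost on osimertinib. If such a patient has no recorded last dose, the date falls back to 1 January, which can precede osimertinib start. No lower bound is stated.

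**Working it through.** The SAP states no follow-up figure, so there is none to reproduce. Its sample size (171/(1 − 0.10) = 190) does not depend on this point.

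**1. Two rules for the same patient**

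| Patient | Follow-up ends (5.3) | Observation ends |
|---|---|---|
| Lost while on treatment | data entry completion | last known alive (5.8) |
| Dead | data entry completion | date of death, collected under 3.5.1 |

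The excess per patient is (data entry completion − death or last-alive date)/30.4375. It is never negative.

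Example with assumed dates: afatinib start 1 June 2014, death 1 September 2016, data entry completed 1 March 2018.

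- Section 5.3 formula: 1369 days/30.4375 = 44.98 months
- Observed to death: 823/30.4375 = 27.04 months
- Excess: 546/30.4375 = 17.94 months

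**2. Size in the cohort (simulation)**

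From the SAP: median 13.6 months on afatinib, 10.1 or 13.2 months on osimertinib (section 5.9), and data entry at least 10 months after osimertinib start (section 3.1.2).

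Assumed: exponential times, no gap between the two drugs, median 9, 12 or 18 months from osimertinib end to death, data entry spread evenly from 10 up to 20 or 27 months after osimertinib start, and 0, 5 or 10% lost at a uniform time between osimertinib start and data entry.

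The formula was compared with the time to the earliest of death, loss and data entry:

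| Quantity | Range over settings |
|---|---|
| Dead before data entry | 14-38% |
| Months counted after death, per dead patient | 6.0-8.7 |
| Months counted after loss, per lost patient | 7.7-9.9 |
| Median follow-up by formula | 28.7-32.8 months |
| Median follow-up observed | 26.6-31.3 months |
| Overstatement within a setting | 0.8-3.6 months |

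**3. Year-only deaths**

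Death in a later year than the last dose is set to 1 January. The error is 0 to 364/30.4375 = 12.0 months, with a mean of about 6.0 if deaths are uniform over the year. Death in the same year as a last dose on 30 June is set to that dose. The error is at most 184/30.4375 = 6.0 months, with a mean of 3.0.

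Deaths recorded before data entry are limited by that date. In simulation (post-osimertinib median 6-18 months) the mean error is then −2.9 to −3.9 months per affected death. The SAP gives no share of year-only deaths. If it were 5-10%:

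- 3-month survival falls by 0.5-2.5 percentage points, and 6-month survival by 0.3-1.4.
- Without censoring, the median shifts by −0.2 to −0.5 months.
- With censoring at data entry, the shift is −0.24 to −0.02 months (true median 6-9), −0.06 to +0.19 (12) and +0.1 to +1.1 (18).

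Each imputed time is too short, but the Kaplan-Meier median is not always shortened.

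**4. Year-only last-alive dates**

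With 5-10% lost, and 10-20% of those lost on treatment having a year-only date, about 0.5-2.6 of 190 patients are affected. Without a recorded last dose, 44-51% of them would be censored before osimertinib start. The primary median moves by −0.01 to −0.10 months.

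**The case against.** The strongest reply is that the formula is explicit, can be programmed, and describes the window of record review, which is potential follow-up. Overstatement is then relative to one definition. Reverse Kaplan-Meier follow-up from afatinib start gave 29.9-38.1 months, above the formula in every setting. No other SAP analysis uses the quantity, and listing L16.2.1.2 shows status with death or loss information, so a reader could recover the alternative. The year-only rule is prespecified, prevents a same-year death from being placed before the last dose, and affects an output that serves neither objective. How often it applies is unknown. The last-alive problem is rare and assumes that the last dose is blank for these patients, although the eCRF is not shown. Section 5.8.1 also allows replacement of patients with many partial dates.

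Much of this stands as to weight: the impact is low, and the second and third parts are minor. The potential follow-up reading does not stand, because the SAP never uses that label and reports the figure beside the deaths. Reverse Kaplan-Meier is a poor benchmark here, since every patient must survive to osimertinib start to be eligible. Replacement does not repair a single year-only death date. Nor is the earliest date needed to keep a death after the last dose: any later date in the feasible interval does that too.

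**Conclusion.** The concern holds. The follow-up formula can never understate observed follow-up, and it overstates it for every patient who dies or is lost before data entry completion. This follows from the text without any assumption. The 0.8-3.6 months on the median rests on the assumed survival after osimertinib, data-entry timing and loss listed above.

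The year-only death rule always yields the shortest admissible time. Its effect on T14.2.3.16 and F14.2.3.17 lies mainly in the early part of the curve and depends on an unknown share of year-only dates. The last-alive rule lacks a lower bound, but its effect on the primary median is at most about 0.1 month under the assumptions used. These are stated rules that give wrong values. They should be corrected, but they do not threaten the primary result.

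**What to change.** 1. **Section 5.3:** end follow-up at the earliest of death, last known alive (if lost) and data entry completion.
2. **Section 5.8.1, year-only deaths:** use the midpoint of the feasible interval, from the later of 1 January and the last osimertinib dose to the earlier of 31 December and data entry completion.
3. **Section 5.8.1, year-only last-alive dates:** use the latest date documented in the eCRF that fits the recorded year, never before osimertinib start or after data entry completion.
4. **T14.2.3.16:** report the number of imputed death dates beside it.

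The cost is SAP wording and minor programming. Every date needed is already collected, and the sample size is unchanged. Reported median follow-up becomes about 1-4 months shorter. The capped midpoint errs slightly upward, by about 0.2-0.7 months per affected death (more if survival is very short), against 2.9-3.9 months downward now. The cap is needed: without it, 10-16% of these deaths would be placed after data entry.
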